#### 5.15 Final Prescription

The final distance prescription of spectacles will be determined on cycloplegic subjective refraction. Masked Optometrist to write final prescription on the clinical examination record (Masked) and take subject, parent and Rx to the unmasked investigator (UI) for lens ordering. The lens will be replaced and upgraded if the equivalent sphere of refraction (SER) is changed by 0.5D or more (or habitual aided LogMAR VA worsen than 0.2) in either eye as

compared with wearing spectacle refraction. The children will be instructed to wear lenses all the time.

If dispensing and frame adjustment are necessary, proceed to spectacle lens dispensing and delivery visit. All dispensing works are performed by UI.

## **6. CLINICAL EXAMINATION BY UMI**

The UMI will be responsible for measuring the aided VA, to check contact lens fitting and related measurement.

### **Objectives:**

- i. to measure aided VA
- ii. to check contact lens fitting
- iii. to modify contact lens fitting and prescription when necessary
- iv. to educate the parents and the subjects how to insert and remove contact lens safety, about lens cleaning and disinfection procedures, etc.
- v. to perform the tests for assessing visual performance of contact lenses
- vi. to ask history, ask the child and parent to sign consent form, fill in questionnaire, etc.
- vii. to maintain integrity of double mask design

Starting from the first 6-month intervals Clinical Examination visit, UMI will be responsible for:

- i. the entry of subject details,
- ii. measurement of aided logMAR VA at distance and near
- iii. checking the contact lens fitting
- iv. checking the contact lenses
- v. re-adjustment of the CL fitting and prescription when necessary
- vi. external ocular health checking
- vii. checking compliance of CL
- viii. collect and check the logsheet about lens wear time and lens compliance
- ix. collect contact lens (to maintain masking) and take the child and parent to masked optometrist

Child and parent will be informed not to raise any questions about contact lenses with the masked optometrist or MI. Those questions should be addressed to the unmasked optometrist or UMI.

### **6.1 Visual performance of spectacle lenses**

#### Objective Visual Assessment

1. Visual acuity in low and high contrast:
  - Distance Log MAR VA High contrast (100%) and low contrast (10%) LogMAR VA will be assessed under both low and low illumination using Logarithmic 2000 series ETDRS Chart and Low Contrast ETDRS Charts at 4 m (Precision Vision Inc.) with

the illuminator cabinet ( $450 \text{ cd/m}^2$ ) respectively. The high and low near VA (40cm) will be measured by the Near Vision Test Card from the Hong Kong Polytechnic University under both high and low illumination.

2. Binocularity:

- Horizontal phoria at distance and near will be measured with Howell-Phoria cards.
- Stereoacuity (minute of arc) will be measured with Randot Stereotest at 40 cm with Polaroid goggles.
- Amplitude of accommodation (D) will be measured with RAF ruler.
- Accommodative Response- Refractive state will be measured by the open-field auto-refractor binocularly with a target 33cm away.

Patient-Reported Measures of Lens Performance

Vision performance and vision comfort with lenses will be graded by the subjects themselves through questionnaires. The subjective rating on vision performance includes vision at distance and near, stability of perceived vision at distance and at near. (Appendix 1)

References

6. Lam CS, [name] WC, Tse DY, [name] YY, To CH. Defocus Incorporated Soft Contact (DISC) lens slows myopia progression in Hong Kong Chinese schoolchildren: a 2- year randomised clinical trial. *Br J Ophthalmol.* 2014;98:40-5.

## 7. Appendix 1

### Questionnaire: Evaluation of a new myopic control lenses

Name: \_\_\_\_\_

Date: \_\_\_\_\_

Record #: \_\_\_\_\_

Section A. Please estimate the time that you spend on the following activities.

#### School time

Hours per day	(a) Weekdays: Mon-Fri	(b) Weekends: Sat -Sun	Hours per day on average = $(5a + 2b)/2$
Wear our spectacles			
Do you wear other optical aids during this study? (e.g. contact lenses, other spectacles, etc.)	Yes (go to Q2)	No	
Contact lenses: _____			
Spectacles: _____			
Near work (e.g. reading, doing homework, smart-phone and i-pads, etc.)			
Mid-working distance activities (e.g. watch TV, computer, playing musical instruments, etc.)			
Outdoor activities			
Indoor activities			
Sleeping time			

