##### With cycloplegia

- Subjective refraction (as reference for the prescription of contact lenses)
- **Objective refraction:** measured by using Shin-Nippon NVision-K 5001 (open-field) autorefractor. Five measurement are obtained for each eye and the average of SER of was used for statistical analysis.
- **AL measurement:** measured by IOL Master (Carl Zeiss). Five measurements were taken and averaged.
- Peripheral refraction: measured by using a Shin-Nippon NVision-K 5001 autorefractor at center, 10, 20 and 30 degrees at the nasal and temporal visual field across the horizontal meridian.
- Dilated fundus examination

Table 4.1 Examination procedures/ items for each visit.

Procedures /measurements	*Screening	Baseline	2 wk	1M	3M	6M	12M	18M	24M
Consent form signed		x							
History-initial	x	x							
History-Update			x	x	x	x	x	x	x
Non-cycloplegic autorefraction	x	x				x	x	x	x
Habitual spec VA	x	x				x	x	x	x
Subjective refraction	x	x				x	x	x	x
Best-corrected VA	x	x				x	x	x	x
Cover test (distance, near)	x								
Phoria (distance and near)		x				x	x	x	x
Lag of accommodation		x				x	x	x	x
Amplitude of accommodation		x				x	x	x	x
Stereopsis		x				x	x	x	x
Pupil size		x				x	x	x	x
Keratometry		x				x	x	x	x
Slit-lamp exam, external ocular health check	x	x				x	x	x	x
IOP measurement	x	x				x	x	x	x
Choroidal thickness measurement		x	x	x	x	x	x	x	x
Eye drops: Anesthetic, Cycloplegics		x				x	x	x	x
Cycloplegic subjective refraction		x				x	x	x	x
Cycloplegic autorefraction		x				x	x	x	x
Axial length measurement		x				x	x	x	x
Peripheral refraction		x				x	x	x	x
Dilated fundus exam		x				x	x	x	x

VA with habitual spectacle			X	X	X	X	X	X	X
Questionnaire of visual habits and spectacle lens performance									X

\* Screening day may be at the same day of baseline measurement.

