### 4.9 Questionnaire

Parents or guardians will be complete a questionnaire regarding the child's vision habits and parents' Rx, and the number of years that the child has been myopic before they enroll in this trial. Questions regarding how much time the children spend reading and outdoor activities will be included. In addition, patient-reported measures on lens performance are also assessed using questionnaire.

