#### 4.11 Statistical analysis

Data of two groups will be presented as the mean  $\pm$  SD. Only data of the right eyes will be used for data analysis if there are high correlation of data between two eyes. Baseline data between two groups between males and female will be analyzed by unpaired t-tests. Welch correction is applied if the difference of SD between the groups is statistically significant.

Primary outcomes

- Changes in auto-refraction (SER in diopters) with cycloplegia

Secondary outcomes

- Changes in axial length (mm) with cycloplegia

1. Repeated measures ANOVAs were used to compare the changes from the baseline visit in SER, and AL over time and between the two study groups in study. Interactions between time and groups were also assessed. If repeated measures ANOVA showed significant results between groups and significant interaction between time and groups, unpaired *t* tests were used to test for differences in SER, AL, between the two groups after the 24-month follow up period, and plots of the change will be plotted for showing trends. Bonferroni corrections were used to take account of *post-hoc* comparisons. The efficacy of myopic control will be determined by dividing the difference in mean SER changes of two groups with the mean SER change in the SV group times 100%.
2. The correlations between changes in Rx, biometric parameters and related factors (e.g. lens wear time, time spent on outdoor activities) are analyzed using Pearson correlations. Multivariate analyses of variance are used to examine the effect on treatment outcomes of various factors, including age, gender, initial refraction, etc.
3. To examine the choroidal response to MD in MS lens, changes in choroidal thickness over time and between two groups will be compared by the same statistically methods used for SER and AL mentioned above (*point 1*). Besides, the correlation between changes in choroidal thickness and axial length will be calculated using Pearson's correlation coefficient. Correlation between the pupil sizes, peripheral refraction and the effect in myopic control in terms of axial length elongation will be calculated using Pearson's correlation coefficient.

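### Both activity tables in Appendix 1 divide weekly hours by 2 instead of 7, so the daily average as printed is 3.5 times too large

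*Combined protocol and SAP*

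**What the plan says.** Appendix 1, Section A, has two tables, one for school time and one for long holidays. Both give the unit of the entries as hours per day. Both have one column headed "a) Weekdays: Mon-Fri" and one headed "b) Weekends: Sat -Sun", and both define the last column as "Hours per day on average = $(5a + 2b)/2". The rows cover wear of the study spectacles, near work, mid-distance activities, outdoor and indoor activities, and sleep. The school-time table also has a yes/no item on other optical aids, which is not averaged.

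Four other places bear on how these hours may be used:

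- Section 4.9, on the questionnaire: "Questions regarding how much time the children spend reading and outdoor activities will be included".
- Table 4.1 lists a "Questionnaire of visual habits and spectacle lens performance" and marks it only at the 24-month visit.
- Section 4.11, point 2, states that correlations between changes in refraction, biometric parameters and "related factors (e.g. lens wear time, time spent on outdoor activities) are analyzed using Pearson correlations".
- Section 6 has the unmasked investigator "collect and check the logsheet about lens wear time and lens compliance", so wear time has a second source.

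Nowhere do the documents give another averaging formula or say that the column is rescaled later.

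**The concern.** An average of weekday and weekend hours must lie between the two. The printed rule equals 2.5a + b, which is larger than both a and b whenever a is above zero. It therefore cannot be a daily average.

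At stake are the exposure hours that the trial would report. Near work (which includes reading) and outdoor time matter most, because section 4.9 names a questionnaire for them and the documents give no other source. Spectacle wear is less exposed because of the logsheet. Means and SDs of hours, any slope per hour and any cut-off in hours per day would be wrong if taken from the column as printed.

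**Working it through.** **Inputs (Appendix 1, Section A, both tables).** a = hours per day, Monday to Friday, 5 days. b = hours per day, Saturday and Sunday, 2 days. Printed rule: (5a + 2b)/2.

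**Correct formula.** A weighted mean is the sum of weight × value divided by the sum of the weights: (5a + 2b)/(5 + 2) = (5a + 2b)/7.

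**Ratio.** [(5a + 2b)/2] ÷ [(5a + 2b)/7] = 7/2 = 3.5, for any a and b that are not both zero.

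**Consistency test.** If a = b = h, a daily average must return h. The printed rule returns 7h/2 = 3.5h; the corrected rule returns 7h/7 = h.

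**Other readings.** A simple mean (a + b)/2 would explain the 2 but not the weights 5 and 2. Taking a and b as weekly totals contradicts the stated unit and would make the multipliers wrong. Neither reading makes the printed rule a daily average.

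**Examples.** The hours are illustrations, not figures from the documents.

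| Activity | a | b | As printed | Divisor 7 |
|---|---|---|---|---|
| Outdoor | 1 | 2 | 9/2 = 4.5 | 9/7 = 1.29 |
| Sleep | 8 | 8 | 56/2 = 28 | 56/7 = 8 |
| Spectacle wear | 10 | 10 | 70/2 = 35 | 70/7 = 10 |
| Spectacle wear | 14 | 14 | 98/2 = 49 | 98/7 = 14 |

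**Which rows give themselves away.** The printed result passes 24 h/day once the true average exceeds 24/3.5 = 6.86 h. Sleep and full-day wear would usually do so. Short rows such as outdoor time would not, so a 24-hour range check would miss them.

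**Effect on the planned correlations.** Multiplying a variable by a positive constant leaves Pearson's r unchanged. A simulated check with 90 records gave r = -0.180 with either divisor.

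**If forms were mixed.** The impossible sleep and wear values might lead some people to correct the divisor and others not. Suppose a proportion p of forms carries F = 3.5 and the rest F = 1, with F independent of true hours and of outcome, and true hours have a coefficient of variation of 0.5 (an assumption). With mean hours set to 1, so that E[X²] = 1.25, r is multiplied by 0.5·E[F] / √(1.25·E[F²] − E[F]²):

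- p = 10%: E[F] = 1.25, E[F²] = 2.125; 0.625/√1.094 = 0.60
- p = 50%: E[F] = 2.25, E[F²] = 6.625; 1.125/√3.219 = 0.63
- p = 90%: E[F] = 3.25, E[F²] = 11.125; 1.625/√3.344 = 0.89

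This shows what mixing would do; nothing in the documents shows that it happened.

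**The case against.** The arithmetic is not in dispute; the case on the other side is that little follows from it.

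- **No planned inference changes.** Under a constant factor the correlations are identical, and so are test statistics in the multivariate analyses. The refraction and axial length comparisons and the sample size do not involve these hours. The plan specifies no descriptive table of hours, slope per hour or cut-off. This stands, and it limits the point to reported hours and to data sets that mix the two rules.
- **Use of the column is not established.** The documents do not say who fills it in, or whether the analysis takes it rather than a and b. This stands, so the consequence is conditional.
- **The error is conspicuous.** Sleep of 28 h/day would probably be noticed. That is likely, but the short rows stay plausible, and piecemeal correction would create the mixing problem.
- **The link from section 4.9 to Appendix 1 is an inference.** Section 4.9 describes a form completed by parents that also covers parental refraction and years of myopia. Appendix 1 has neither item, and section 6.1 cites it only for lens performance, so a further form may exist. However, the single questionnaire row in Table 4.1 joins visual habits with lens performance, which matches Sections A and B of Appendix 1. The link is likely, not stated.
- **The text was machine-read.** A misread digit cannot be wholly excluded, but the same divisor appears in both tables.

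**Conclusion.** The concern holds. The averaging rule on the trial's own data form is wrong as written, in both tables, by an exact factor of 3.5 on every row where hours are entered. That result rests only on the table headings: hours per day, five weekdays and two weekend days.

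The practical effect depends on the column being filled in and used as printed. In that case the reported hours are wrong, while Pearson correlations are unaffected as long as all forms follow the same rule. The primary and secondary treatment comparisons are untouched, and the correct averages can be recovered from a and b. It should be corrected, but it does not threaten the main result.

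**What to change.** Change the divisor to 7 in both column headings. Alternatively, drop the third column, collect only a and b, and compute (5a + 2b)/7 centrally. For forms already completed, recompute every row from a and b and disregard the handwritten average.

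As a data check, flag any recorded average larger than both a and b. This misses rows with a = 0, where the printed rule returns b itself instead of 2b/7, so the recomputation should cover all rows and not only the flagged ones. It would also help to state in section 4.11 that the hours analysed are computed from a and b, and from which form.

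The cost is one character in two headings and a recalculation from values already on the form. No new data are needed.

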### Long holidays

Hours per day	(a) Weekdays: Mon-Fri	(b) Weekends: Sat -Sun	Hours per day on average = $(5a + 2b)/2$
Wear our spectacles			
Near work (e.g. reading, doing homework, smart-phone and i-pads, etc.)			
Mid-working distance activities (e.g. watch TV, computer, playing musical instruments, etc.)			
Outdoor activities			
Indoor activities			
Sleeping time			

### Section B.

Please rate the performance of your current spectacles. (Please circle the choice and rating)

		Poorest	→	acceptable	→	Fair	→	→	Good	→	Excellent
1	Vision at distance (clarity)	1	2	3	4	5	6	7	8	9	10
2	Vision stability at distance	1	2	3	4	5	6	7	8	9	10
3	Clarity of vision for intermediate distance (e.g. computer, watching TV)	1	2	3	4	5	6	7	8	9	10
4	Clarity of vision for near tasks (e.g. reading, using smartphone)	1	2	3	4	5	6	7	8	9	10

5	Vision stability at near	1	2	3	4	5	6	7	8	9	10
6	Vision comfort	1	2	3	4	5	6	7	8	9	10
8	Vision during outdoor	1	2	3	4	5	6	7	8	9	10
9	Easiness of lens adaption	1	2	3	4	5	6	7	8	9	10
10	Overall performance	1	2	3	4	5	6	7	8	9	10

**Do you have the following symptoms when wear this spectacles?**

		Never	→	Seldom	→	Some-times	→	→	Often	→	Always
1	Blurred vision at far distance	1	2	3	4	5	6	7	8	9	10
2	Blurred vision at intermediate distance (e.g. computer)	1	2	3	4	5	6	7	8	9	10
3	Blurred vision at near (e.g. reading, smart-phone)	1	2	3	4	5	6	7	8	9	10
4	Ghosting image	1	2	3	4	5	6	7	8	9	10
5	Unstable vision at distance	1	2	3	4	5	6	7	8	9	10
6	Unstable vision at near	1	2	3	4	5	6	7	8	9	10
7	Difficulty or slowness in	1	2	3	4	5	6	7	8	9	10

	refocusing your eyes from one distance to other										
8	Eyestrain	1	2	3	4	5	6	7	8	9	10
9	Double vision	1	2	3	4	5	6	7	8	9	10
10	Dizziness	1	2	3	4	5	6	7	8	9	10
11	Headache	1	2	3	4	5	6	7	8	9	10

Other comments:

---
